The objective of this proposal is to adapt PPE training guidelines issued by the World Health Organization (WHO)³⁶ and the U.S. Occupational Safety and Health Administration (OSHA)³³ for use by healers and to fill the current evidence-to-practice gap by comparing effectiveness of two practical strategies for implementing evidence-based PPE guidelines.

Our proposal compares two implementation strategies to increase PPE use and proper disposal during procedures and decrease the number of risky injections performed (de-implementation of traditional injections): (1) Health care worker (HCW)-led education on blood exposure risk and PPE use through a week-long training, followed by three educational outreach visits at the healer's place of practice vs. (2) "Early adopter" healer³⁷⁻⁴⁰ and HCW co-led training followed by three educational outreach visits. We hypothesize that "early adopter" healer messaging and delivery will have greater impact given their membership within the healer community.

Aim 1. Gather information about how healers and health care workers are learning about PPE use to develop an acceptable and appropriate PPE training program.

Aim 2: Compare fidelity to delivery of PPE training between the HCW-only and the healer plus HCW teams.

We will compare training fidelity of the two teams via three constructs: (1) content, (2) coverage, and (3) duration^{41,42} to determine if there is a difference in fidelity between the two types of teams.

Hypothesis 1: Training fidelity will be greater among healer + HCW teams, as they will have greater motivation to comprehensively deliver education and skill building sessions to healers.

Aim 3: Compare the effects of the two implementation strategies on healer exposure to patient blood.

We will enroll traditional healers into each PPE strategy using a stratified random sampling. Healers will use containers to collect all used sharps and used gloves over a six-month period and complete a low literacy data collection form to document glove use to identify gaps in PPE use.

Hypothesis 1: Healers who are trained by the healer + HCW team will have a higher proportion of glove use during injections than those in the HCW-only trainer arm.

4. Study Population

Population

Traditional healers and biomedical practitioners (including clinicians and nurses) providing patient care in the Bushbuckridge area.

Inclusion Criteria

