Aim 3: From preliminary data collected from healers in Agincourt in 2019, the median proportion of glove use during vaccinations was 0.44, mean 0.39, and standard deviation (SD) 0.39. Our sample size is calculated based on a two-sample t-test and incorporates these preliminary data. Assuming the SD=0.39, then we anticipate needing 61 healers per arm (total of 122) to have 80% power to detect at the ($\alpha=0.05$ -level) a difference of 0.2 in the proportion glove use between the HCW-only and the healer + HCW teams (e.g., 0.4 vs. 0.2). Included below is the variability in power given different deltas (differences in the mean proportion of blood exposure between the two arms) (Table 1). Note, that these power calculations are approximate as primary analyses will be performed using negative binomial regression. Power calculations using negative binomial regression would require assuming a distribution of the offset (number of procedures performed per healer), which substantially complicate the calculations. Therefore, we present power calculations based on two-sample t-tests, which should be fairly similar.

Table 1 Sample Size and Power

N	Δ	SD	α	P
61	0.17	0.39	0.05	66.57
61	0.18	0.39	0.05	71.52
61	0.19	0.39	0.05	76.08
61	0.20	0.39	0.05	80.22
61	0.21	0.39	0.05	83.89

61	0.22	0.39	0.05	87.08
61	0.23	0.39	0.05	89.81
61	0.24	0.39	0.05	92.09
61	0.25	0.39	0.05	93.96

N: number of healers per arm

Δ: Difference to detect (delta)

SD: Standard deviation

α: Significance level (alpha)

P: Power, %

Randomization strategy

To avoid concerns that, despite randomization, one intervention arm of healers will substantially differ from the other, we will conduct stratified randomization. Specifically, we will stratify based on healer sex and the number of patients seen in a given month (dichotomized into high/low based on the estimated median number of patients seen in the past month). This will result in 4 strata. At the time of randomization, each healer will be put in a strata and equal numbers of healers in each strata will be randomized to the two intervention arms.

5. Methods

Measurement of Results

Aim 1: We will use qualitative measures to understand the best strategies to delivery PPE training to traditional healers in Bushbuckridge.

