Our intervention arm will receive the same training and educational outreach as the control arm, but with training and outreach conducted by a clinical team that includes healers who adopted and use PPE on their own (early adopters).³⁷⁻⁴⁰ Early adopters are people who identify a new behavior as innovative (i.e. use of latex gloves) and adopt this behavior before the majority of their colleagues. Used primarily in the Diffusion of Innovation Theory⁵² to explain adoption of new behaviors, we hypothesize that the strategy of engaging early adopting healers as trainers in collaboration with HCWs will increase peer pressure, perceived tension for change, participant self-efficacy, and acceptability of PPE use among healers who do not use any barrier to blood exposure. Early adopters can achieve this by highlighting relative advantages, compatibility with their role of a traditional healer and leader in the community, simplicity, and ease of trialability of using gloves with patients.⁵²

Participants will receive a baseline and end line (7 months post- training) HIV test (to detect any seroconversion events and to determine if those living with HIV are as motivated to use PPE as those who are HIV-negative). Participants will also complete baseline and end line surveys to assess their knowledge, motivation, and behavioral skills to determine the impact of training on the healer. Once a month, a study assistant will visit each healer to collect all used sharps and PPE; three times during the study the study assistant will also conduct observations of healers using PPE to determine if they are using it correctly post-training.

Healers and healer care workers who are selected, consent and contribute to the training of healers will be reimbursed for their transportation to the training venue and provided with a small token of appreciation (a voucher to a local store for R150) at the conclusion of the workshops.

6. Study Location

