Analysis plan for coverage: We will calculate the percentage of sessions completed as the actual number of sessions completed for a participant divided by the total number of planned sessions. The percentage of sessions completed between the two intervention arms will be compared using mixed effects Poisson regression with the number of planned sessions (in most cases 3) as an offset. 95% confidence intervals will be constructed. The models will include random effects for the trainers. Covariates will include patient volume, sex, and baseline age. Missing data and LTFU will be handled as described above.

Aim 3: The analysis will follow intent-to-treat protocol. Our primary outcome is the proportion of a healer's procedures that were conducted using latex gloves (numerator = number of procedures with blood exposure, denominator = number of procedures). We will compare the blood exposure proportions between the two study arms using a negative binomial regression model. In the negative binomial regression, the outcome will be the number of times gloves were used and the number of procedures performed by the healer (number of razor blades) will be included as an offset. Such an analysis is appropriate because it properly accounts for heterogeneity between healers in the number of procedures performed, and the resulting estimates from the model can be interpreted as relative proportions (proportion of procedures with blood exposure in Arm 1 vs. proportion of procedures with blood exposure in Arm 2). In addition to our primary intervention

exposure variable, we will include healer sex and baseline age as covariates in our model. Sensitivity analyses will compare blood exposure proportions between the two intervention arms using a two-sample t-test; a Wilcoxon rank sum test will be fit as needed to avoid normality assumptions.

Based on prior experience working with healers, we anticipate very low rates of loss to follow-up (LTFU). Healers who are LTFU will be censored at the time of their last recorded data collection, and inverse-probability of censoring weights based on healer characteristics randomization will be used, if necessary, to account for differences between healers who are LTFU and those who remain in the study. Missing data will be imputed using chained equations and 20 imputation replications.

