The secondary outcome, proportion of injection events, will be analyzed in a manner identical to that of our primary outcome except the outcome will be the total number of skin-cutting events performed by the healer, regardless of the use of PPE. A negative binomial regression model will be fit using the number of overall procedures as an offset. While we will not specifically look at HIV seroconversion as a study outcome, we will assess healers' baseline and end line HIV status for ethical reasons. Historical data show that the one-year incidence rate of HIV seroconversion is 1.7%. Since the incidence rate is low, we will likely not have adequate power to see a difference between intervention arms, but this information will allow us to appropriately power our subsequent R01 trial.

A separate analysis will assess each strategies' effect on PPE self-efficacy, PPE knowledge/skills, and accurate risk assessment post-training. We will explore whether the intervention effects on these measures differ by a) trainer fidelity to the intervention and/or trainer identity (healer vs. clinician), respectively. These analyses will provide quantitative data to revise and refine, as needed, the intervention for evaluation in a large RCT effectiveness study as a means of improving prevention engagement while reducing stigma.

8. Ethical Considerations

Recruitment and Consent

Aim 1: *Traditional healers* from the target community will be recruited via two strategies: (1) Healers in target catchment area are currently being mapped by two students (one from Vanderbilt and one from University of Witwatersrand). The healers are providing their address/location and contact information (phone numbers, contact for other family members) for use in future activities (including research endeavors). The healers will be contacted and given general information about the proposed study. All healers will be invited to community meetings where more information about the study procedures and aims will be provided. (2) The Kukula Traditional Healers association- the primary healer organization in the region- will hold 3 meetings to recruit healers interested in participating. Healers who express interest will be given the option for dates/locations where we will conduct recruitment fairs or the option to have a study assistant visit them at home. All recruitment will be conducted in a private room or at the home of the healer (as per the participants preference).

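### The plan describes no pre-training injection count, so the between-arm comparison of skin-cutting events forgoes a likely strong predictor; the loss is precision and chance balance, not validity.

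*Combined protocol and SAP*

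**What the plan says.** Section 2 (Objectives) gives the two strategies a second purpose besides PPE use: to "decrease the number of risky injections performed". Section 7 (Data Analysis, Aim 3) defines the secondary outcome accordingly: "the outcome will be the total number of skin-cutting events performed by the healer, regardless of the use of PPE". It is to be analysed in the same way as the primary outcome, by negative binomial regression, with overall procedures as the offset. The Aim 3 covariates are healer sex and baseline age. Patient volume is a covariate in the Aim 2 models but is not listed for Aim 3.

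Section 4 (Randomization strategy) says "we will stratify based on healer sex and the number of patients seen in a given month", with volume "dichotomized into high/low based on the estimated median number of patients seen in the past month", and "equal numbers of healers in each strata will be randomized to the two intervention arms".

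Section 5 has healers collect sharps and record injections during the six trial months; no run-in is described. The described baseline contact is an HIV test plus a survey: "Participants will also complete baseline and end line surveys to assess their knowledge, motivation, and behavioral skills". The printed items in Appendices 3 and 4 include no injection count, and Appendix 1 is the Aim 1 interview guide. Eligibility requires that a healer performs traditional vaccinations, with no minimum number.

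**The concern.** The plan recognises that healers differ in volume. It justifies the offset in the glove-use model because "it properly accounts for heterogeneity between healers in the number of procedures performed", and it stratifies because it fears the arms may differ despite randomisation. For the injection outcome, however, the only volume measure is patients seen for any reason, reduced to high or low, and even that is not in the Aim 3 model. Two healers with the same patient load can differ widely in how many injections they give.

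If injection numbers vary mainly between healers, a healer's own prior count should predict the six-month count well. Without it, the interval for the arm comparison is wider than it need be, and a chance difference in prior volume can resemble or mask an effect on injections. A pre-training count that was not collected cannot be recovered once training has begun.

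**Working it through.** **1. The plan's own figure.** Table 1 gives 80.22% power for a glove-use difference of 0.20, SD 0.39, 61 per arm, alpha 0.05. The noncentrality is 0.20 / (0.39 × √(2/61)) = 0.20 / 0.0706 = 2.83; a two-sided t-test on 120 df gives 80.22%, so the figure reproduces. It concerns glove use only. No power figure is given for injections.

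**2. Inputs for the injection comparison.** From the documents: 61 healers per arm. I take 80% power and two-sided 5%, as in Table 1. Assumed, because the documents give neither: SD of the log injection count 0.9 (range 0.6 to 1.2), and correlation ρ between log baseline and log follow-up count of 0.3 to 0.7. The calculation is for a count compared without an offset and gives the existing stratum no credit.

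**3. Formulas.** SE of the log ratio = SD × √(1 − ρ²) × √(2/61), with √(2/61) = 0.181. Detectable reduction = 1 − exp(−2.80 × SE), where 2.80 = 1.96 + 0.84. Equivalent healers per arm = 61 / (1 − ρ²).

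At SD 0.9:

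| ρ | SE | Detectable reduction | Equivalent n per arm |
|---|---|---|---|
| 0 (no baseline) | 0.163 | 36.6% | 61 |
| 0.3 | 0.155 | 35.3% | 67 |
| 0.5 | 0.141 | 32.6% | 81 |
| 0.7 | 0.116 | 27.8% | 120 |

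The SE falls by 5%, 13% and 29% respectively (1 − √(1 − ρ²)). At SD 0.6 the detectable reduction goes from 26% to 25–20% over ρ 0.3 to 0.7; at SD 1.2 it goes from 46% to 44–35%.

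**4. Chance imbalance.** At SD 0.9, the between-arm ratio of prior volume has a 95% chance range of exp(±1.96 × 0.163) = 0.73 to 1.38 if the strata explain nothing.

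**5. What the existing stratum could explain.** Under normality a median split keeps √(2/π) = 0.798 of a correlation. If patients seen and injections correlate at 0.3, 0.5 or 0.7, the split explains (0.798 × correlation)² = 6%, 16% or 31% of the variance in injections. A baseline count explains ρ² = 9%, 25% or 49% at ρ = 0.3, 0.5 or 0.7. The two overlap, so the gain over a model that also used the stratum would be smaller than in step 3.

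**6. Dependence on the offset.** The secondary model has overall procedures as its offset.
- If that means all treatments, the modelled quantity is injections per treatment. The SD and ρ above do not apply, and the matching predictor is a baseline rate rather than a count.
- If it means razor blades, as procedures does in the primary analysis, events divided by offset is about 1. There is then no comparison of injection numbers for any covariate to sharpen.

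**The case against.** The strongest reply is that the figures belong to an analysis the plan does not specify. They use raw counts, whereas the plan names an offset that, if it means all treatments, may already remove much of the volume variation. They also rest on an SD and a correlation that no document supplies, and they give the patient-volume stratum no value. At ρ = 0.3 the gain is slight. All of this stands: the numbers show direction and possible size and are not a forecast.

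Four stronger readings are tempting, and the documents do not support them.

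- **That no baseline injection count is taken.** The baseline survey is not printed in full. Part A of Appendix 3 is headed as examples, and the patients-per-month question that stratification needs is not printed either. One can say only that no count is described.
- **That the comparison is biased.** Allocation is randomised, and the confidence interval already allows for chance differences between arms.
- **That a decrease has no starting point.** The trial compares two strategies, so the contrast is between arms and needs no baseline. One month's recall against six months of razor-blade counts would not make a sound before–after measure anyway.
- **That injections should replace patients as the stratifier.** The sample size and the Aim 3 hypothesis concern glove use, and patient volume also serves Aim 2. Changing a trial-wide stratifier for one secondary outcome is a debatable trade, and a covariate should give most of the precision without it.

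None of this removes the case for the added question and covariate. The question precedes allocation, so it cannot bias the comparison, and it can be matched to whichever scale the secondary model uses.

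**Conclusion.** The point holds as a missed gain in precision for a secondary outcome tied to a stated goal. The plan describes no pre-training injection count, and its Aim 3 models use no volume covariate. Validity is not in question, and the primary sample size of 61 per arm is unaffected.

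The possible gain runs from slight to substantial under the assumptions in the working. It applies as calculated only if injection counts are compared without an overall-procedures offset. On a per-treatment scale the size is unknown, and with a razor-blade offset the model needs correcting before precision matters.

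**What to change.** Keep the current stratifiers. At the pre-randomisation contact that asks about patients seen in the past month, also ask how many traditional vaccinations (injections) the healer performed in that month. If the unprinted baseline survey already asks this before allocation, say so and use it.

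Define the offset of the secondary model, then enter the baseline value as a covariate on the same scale:

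- counts compared without an overall-procedures offset: log(baseline injections + 0.5);
- an offset of all treatments kept: the log of baseline injections per patient seen, with a small constant specified in advance for zeros;
- an offset meaning razor blades: correct the offset first.

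The cost is one enrolment question and one model term, with no added visits, staff or healers. The downside is recall error, which only reduces the gain.

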Aim 2: We will rate training fidelity via two constructs: (1) content and (2) coverage^{41,42} during the week-long training session and community-based outreach sessions (Appendix 2). Understanding the fidelity of training delivery is essential to interpreting the effect of the intervention on PPE behavior change. If HCW + healer teams can deliver training with greater or equal fidelity than HCWs alone, PPE training can be more quickly scaled up nationwide (given the large number of healers) and conducted at lower cost (healers charge considerably less per hour than HCWs). We believe that the healer + HCW teams may have more motivation to deliver the program with fidelity during community-based sessions than the team of HCWs alone because of healers' desire to protect their peers living in their own community. Three HCWs who volunteer to work on this project will be randomly assigned to the intervention team (along with the healers), with six volunteer HCWs assigned to the control arm.

Aim 3: Healers will complete an interviewer-assisted survey immediately post training (Appendix 3) using the Consolidated Framework for Implementation Research framework⁴³ (compatibility of PPE with current behavior, peer pressure to use PPE, perception of the inclusiveness of the training process, cost) and individual characteristics from the situated-IMB model (Figure 3)^{44,45}. During the six months of the trial, healers in each arm will record data on our primary outcome: the proportion of injections conducted using PPE in two ways.

(1) Collect used sharps and PPE. Healers will be given containers to place all used gloves and razors/sharps to both ensure healer safety and allow us to count materials used (healers use gloves and a single razor once per patient and subsequently throw them into latrines or trash piles). We will use the *number of glove pairs as the numerator* (number of times they used gloves during procedures) and the *number of razor blades as the denominator* (number of injections given). While some may be concerned with social desirability bias, healers have been told for years to use gloves and were very open with us about their non-use. Healers have no reason to

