Aims 2 & 3: Traditional healers randomized to both the control and intervention arms will receive PPE education and training, general HIV prevention education and skill building (including condom use, positive prevention, and pre-/post-exposure prophylaxis services), and three educational outreach and coaching visits at the healer's place of practice to provide on-the-ground advice and support for PPE use. These training and educational outreach sessions are designed to allow healers to receive education about bloodborne disease transmission (information), accurately assess their risk of contracting bloodborne illness (motivation), and develop skills to effectively don, doff, and dispose of used PPE (behavior) (Appendices 2 and 3). Outreach visits will focus on delivering five key messages and troubleshoot any issues healers may have in following recommendations. We will assess the impact of our evidence-based PPE intervention on the knowledge, motivation, and behavioral skills developed by traditional healers using the Situated Information Motivation and Behavioral Skills (Situated-IMB) model.⁴⁴ The use of in-class

and educational outreach strategies have yielded improvements in clinical care delivery,⁴⁶⁻⁴⁸ including use of PPE,⁴⁹ among physicians, nurses, and community health workers in low-resource settings. These strategies were selected in consultation with traditional healers in Agincourt who reported never having received training on how to protect themselves from exposures based on the strategies used around the world to train health care providers to avoid infection.^{33,36,49-51} PPE use is feasible and acceptable to most healers and their patients already,²⁷ but they lack the knowledge and/or motivation to use gloves properly and regularly.

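### Nothing keeps gloves and blades used under study observation out of the primary counts; if counted, they pull the glove-use ratio towards 1

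*Combined protocol and SAP*

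**What the plan says.** Section 5, Measurement of Results, Aim 3, sets up the count: "Healers will be given containers to place all used gloves and razors/sharps". Glove pairs form the numerator and razor blades the denominator. Section 7, Data Analysis, Aim 3, models the number of gloved procedures by negative binomial regression with the blade count as offset, and reports a relative proportion.

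Section 5, Study Procedures, Aims 2 & 3, has the study assistant collect all used sharps and PPE every month. It then states that "three times during the study the study assistant will also conduct observations of healers using PPE to determine if they are using it correctly". The same section describes training and outreach sessions in which healers are to "develop skills to effectively don, doff, and dispose of used PPE".

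None of these places says what happens to gloves or blades used while the study is observing or coaching. Neither the container count nor the healer's own record of injections has a flag for them.

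Measurement of Results does address social desirability. It argues that healers have been open about not wearing gloves and would gain nothing by inflating their use, since that would mean buying blades or travelling for gloves.

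**The concern.** The primary outcome is meant to describe routine behaviour. An observation of PPE use is an occasion created by the study, and its purpose makes glove use likely. If its gloves and blades go into the container, they are counted as routine practice in both arms.

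The plan's answer on social desirability concerns healers altering their own unobserved counts. It does not cover gloves worn because someone has come to watch them being worn.

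At stake is the size of the main estimate. Adding the same study-prompted glove use to both arms makes the arms look more alike than routine practice is. Once the items are mixed in a container they cannot be told apart, so the analysis cannot repair this later.

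**Working it through.** **Inputs from the plan.** Section 4, Aim 3: "Assuming the SD=0.39, then we anticipate needing 61 healers per arm (total of 122) to have 80% power" for a difference of 0.20, illustrated as 0.4 against 0.2. Allocation is 1:1. Section 5: three observed occasions per healer.

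**Inputs assumed.** One injection is seen per occasion, so three per healer. N is the number of counted injections per healer over six months; it is not the N of Table 1, which counts healers. The plan does not give it, so I use 20 to 300. Observed glove use q is the same in both arms, and N is similar across healers.

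**The plan's own figure.** A two-sample t-test with two-sided alpha 0.05, SD 0.39, difference 0.20 and 61 per arm gives power 80.22%. This agrees with Table 1, as do its other eight rows.

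**Case A: observed real injections are counted.** Let f = 3/N and let p be routine glove use. Each arm's counted proportion becomes f·q + (1 - f)·p. Subtracting, the term f·q cancels:

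difference = (1 - f) × (0.4 - 0.2) = (1 - 3/N) × 0.20, whatever the value of q.

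The ratio does depend on q. With q = 1 at N = 20, f = 0.15. The arms become 0.15 + 0.85 × 0.4 = 0.49 and 0.15 + 0.85 × 0.2 = 0.32, so the difference is 0.17 and the ratio 1.53.

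**Case B: demonstrations without a blade, gloves counted.** Three pairs enter the numerator only. Each proportion becomes p + 3/N, so the difference stays at 0.20 for equal N. The ratio is (0.4N + 3)/(0.2N + 3); at N = 20 this is 11/7 = 1.57.

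| N (assumed) | A: arms (q = 1) | A: difference | A: loss | A: ratio | B: ratio |
|---|---|---|---|---|---|
| 20 | 0.32, 0.49 | 0.170 | 15% | 1.53 | 11/7 = 1.57 |
| 30 | 0.28, 0.46 | 0.180 | 10% | 1.64 | 15/9 = 1.67 |
| 60 | 0.24, 0.43 | 0.190 | 5% | 1.79 | 27/15 = 1.80 |
| 120 | 0.220, 0.415 | 0.195 | 2.5% | 1.89 | 51/27 = 1.89 |
| 300 | 0.208, 0.406 | 0.198 | 1% | 1.95 | 123/63 = 1.95 |

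**If observed glove use is below 100%.** With q = 0.7 at N = 60, the arms are 0.035 + 0.19 = 0.225 and 0.035 + 0.38 = 0.415. The difference is still 0.19 and the ratio is 1.84.

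**Power.** In Case A with a common f, the between-healer SD shrinks by the same factor. The standardised difference 0.20(1 - f)/[0.39(1 - f)] = 0.513 is unchanged, and power stays at 80.22%. In Case B with equal N, a constant is added to every healer, which changes neither the difference nor the SD.

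**Which outcome.** These ratios are for glove use, the count named for the regression. Section 7 also calls the outcome blood exposure. If ungloved procedures were modelled instead, Case A with q = 1 at N = 20 gives 0.85 × 0.6 = 0.51 against 0.85 × 0.8 = 0.68. That ratio, 0.75, is the same as 0.6/0.8, although the difference still shrinks to 0.17.

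**The case against.** The strongest reply is that the plan does not say that patient injections are observed. It does not say who supplies the gloves at these visits or where they go afterwards. The technique checklist in Appendix 4 is scored against a scenario and covers gowns, masks and eye protection, which suits a staged check at least as well. It is headed for the end of training, so its use at the three visits is itself unstated. If the assistant brings the gloves and takes them away, there is nothing to correct.

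This stands as a limit on certainty, so the point is conditional. It does not remove it: the containers are for all used items, and both a real injection and a demonstration lower the glove-use ratio if the items are counted.

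The reply is also right on size. The effect is small at high volume. The low-volume figures are the least secure, because a healer who injects rarely is unlikely to have a patient present on all three visits unless the visits are timed to patients. A reader might imagine a healer whose only three injections were all observed and who scores 100%. That is an extreme case which nothing in the plan makes likely.

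A reader might also infer that the trial loses power. The documents give no distribution of volumes to show this. An illustrative simulation with widely varying volumes did show lower power, but it gave every healer exactly three observed real injections, so I do not rely on it.

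Finally, a reader might infer that success in reducing injections would undermine the primary outcome. A smaller N does raise 3/N, but the plan gives no volume or expected reduction from which to size this.

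**Conclusion.** The point holds in conditional form. Read literally, the plan counts all container material and makes no exception for study-prompted use. If observed items reach the container, the glove-use ratio moves towards 1. In the real-injection case the absolute difference also shrinks, by 15% at 20 injections per healer, 5% at 60 and 1% at 300. In the demonstration case it does not shrink when volumes are equal.

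The result rests on three counted occasions per healer, equal observed glove use and similar volumes in both arms, and a volume range that is assumed. Under those conditions the bias is towards no difference and would not by itself create a false positive. The documents do not support saying that observed injections certainly enter the counts, that glove use under observation is near certain, or that the planned power is lost. This is a worthwhile, inexpensive improvement to the outcome definition; it does not invalidate the design.

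**What to change.** In Section 5 (Study Procedures, Aims 2 & 3), state whether the three observations are of real injections or demonstrations. There and in Section 5 (Measurement of Results, Aim 3), state that gloves and blades used during a study observation, outreach visit or demonstration are bagged separately by the visiting team or marked on the data collection form. In Section 7 (Data Analysis, Aim 3), leave these items out of both the numerator and the denominator of the primary outcome, and report the count of all material as a sensitivity analysis. Observed procedures would still serve the assessment of correct use. The rule must be in place before collection starts.

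The cost is a separate bag or a mark at visits that already take place, and a line in the collection instructions. Up to about three observed procedures per healer leave the count, plus any injection performed at an outreach visit. A healer with no other procedures would contribute no primary data.
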